The Coach Mpilo Study Protocol

Title: The Coach Mpilo Study: evaluation of a peer-led intervention to promote engagement in HIV care for men living with HIV in South Africa

Funding organisation: Fund for Innovation in Development

Grant type: Stage 2: Test and Position for Scale Grants

Project Team

Principal Investigators

[name] (University of Cape Town)

[name] (University of Pennsylvania)

Co-Investigators

[name] (University of Cape Town)

[name] (University of Cape Town)

[name] (University of Pennsylvania)

[name] (University of the Witwatersrand)

External advisors

[name] (University of Cape Town)

[name] (South African Medical Research Council)

[name] (Brown University)

[name] (Desmond Tutu Health Foundation)

[name] (Population Services International)

[name] (Population Services International)

[name] (Matchboxology)

Core evaluation team

[name] (Abdul Latif Jameel Poverty Action Lab)

[name] (Abdul Latif Jameel Poverty Action Lab)

[name] (Abdul Latif Jameel Poverty Action Lab)

Project Summary

Developed in South Africa using extensive input from community members and healthcare professionals, Coach Mpilo is a peer support intervention that was designed to improve health outcomes for men living with HIV. Coach Mpilo engages men living with HIV as coaches who provide support to their peers and help them address psychosocial barriers in accessing and staying in HIV care.

The peers employed by Coach Mpilo provide individualized assistance to men who are struggling with medication adherence and clinic visits, focusing on specific barriers ranging from knowledge about the benefits of HIV treatment, stigma, mental health, and social isolation.

Through a randomised control trial, this project will (1) determine the impact of the Coach Mpilo intervention on retention in HIV care, viral suppression, HIV treatment adherence, mental health, HIV stigma, and economic status; (2) identify populations of men who may not benefit from the intervention and require alternative support; and (3) assess the intervention's cost-effectiveness.

Background

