IDI procedures and data management. We will obtain written informed consent before IDIs. IDIs will be conducted by trained interviewers, in participants' preferred language (Zulu/English), and in a private and safe location. Procedures for data quality assurance will include: (1) careful design of IDI guides; (2) extensive interviewer training; and (3) immediate analysis of data to inform improvements for subsequent interviews. IDIs will last approximately 1-1.5 hours and be recorded using a digital voice recorder. Audio files will be translated and transcribed verbatim by a transcriptionist. After transcription, the study team will edit out any personal identifying information. Participants will receive ZAR200 (USD11.50) in grocery vouchers for completion of the IDI.

Analyses: Primary quantitative analysis. Among Aim 1 intervention group participants we will evaluate factors associated with declining the offer of a coach using logistic regression, with independent variables including socioeconomic and demographic characteristics, local clinic, internalized stigma, HIV-status denial, symptoms of mental distress and ART readiness. Secondary within-group analyses of retention on ART using unsupervised machine-learning clustering methods will be conducted to determine the populations of men whose outcomes are least improved by engagement with a coach.¹⁴ We will analyze the composition of each cluster and the association between sub-group classification and the outcome of receiving the intervention but not being retained on ART, i.e. who does not respond well to the program?

Qualitative data analysis. We will conduct ongoing saturation analyses, based on iterative coding during data collection. Transcriptions will be checked for accuracy and entered into Dedoose. We will also enter all observational notes as memos. Data analysis will be iterative, and include both deductive and inductive approaches to thematic analysis. To ensure accurate interpretation, we will conduct independent reviews of transcripts to generate an overarching thematic framework for data interpretation. The investigators will compare frameworks for consistency and discrepancies. Data will be re-examined, allowing for discussion and making interconnections between research questions, coding categories, and raw data.

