Expected outcomes. Findings from Aim 2 will advance our understanding of the uptake and impact of peer-led interventions for people living with HIV. Crucially, we will identify populations of men who do not respond to the Coach Mpilo program. We will gain insights from both recipients of the intervention and coaches on perceived efficacy and underlying mechanisms for intervention effects determined in Aim 1. Findings will inform intervention scale-up and modifications to the program for maximum impact.

IDI quality assurance: We will monitor depth of discussions through immediate review of interview materials, and if necessary, refine probes in the IDI guides, and conduct additional interviewer training.

Aim 3: Assess the cost-effectiveness of the Coach Mpilo program

To inform strategic policy decisions about the scale-up of Coach Mpilo, and how it compares in cost and cost-effectiveness against current standard of care treatment, as well as other HIV interventions, we will conduct an economic evaluation. We will collect cost-related data and resource utilization data to construct cost estimates for both arms. These data will be combined with retention in care data from Aim 1 to determine average costs per client retained in care and incremental cost per additional person retained. As part of the analysis, we will conduct a sub-analysis to adjust the cost estimates to reflect implementation in a routine care setting, excluding research-related expenses such as start-up and study-specific costs. This will provide more realistic national-level scale-up cost estimates for Coach Mpilo. Epidemiological modeling based on effectiveness estimates from Aim 1, will use the Thembisa model¹⁵ to estimate several long-term health outcomes, including life years saved and HIV infections averted due to onward transmission. These long-term health outcomes will form the basis to estimate the cost-effectiveness analysis of Coach Mpilo. To compare Coach Mpilo to other HIV prevention and treatment options in South Africa with the broader aim of informing strategic policy decisions, we will incorporate our estimates into the South Africa HIV Investment Case, a prominent initiative that assesses the relative cost-effectiveness of different HIV interventions and aims to inform government of the optimal mix of interventions that also accounts for allocative efficiency.

Cost and resource use data sources

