Outcomes: We will estimate the total cost and average cost per person in treatment, and the cost per person successfully retained in HIV care at 12 months for both the Coach Mpilo and the standard of care study arms. Additional outcomes will include the intermediary cost-effectiveness outcomes of incremental cost per additional participant retained, and long-term cost-effectiveness outcomes from modelling work will include incremental cost per life year saved and incremental cost per HIV infection averted.

Expected outcomes: Our findings will add to the limited evidence on the cost-effectiveness of peer-led interventions for people living with HIV. They will also indicate the role of peer-led interventions in closing the gender gap in ART coverage and viral suppression rates. Finally, they will be directly useful for decisions about whether to allocate scarce resources to Coach Mpilo, or whether the use of the intervention should be more narrowly targeted to specific population segments.

Aim 4: Assess the acceptability, feasibility and fidelity of the Coach Mpilo program

To inform intervention refinements and policy decisions on the scale-up of Coach Mpilo and peer-led interventions more generally, we will quantitatively and qualitatively assess implementation outcomes alongside effectiveness and cost-effectiveness of the intervention. Implementation outcomes are viewed as important for evaluation of complex health interventions in research and practice,¹⁶ providing indications into the implementation process as preconditions for attaining intended intervention engagement and health outcomes.¹⁷ Table 2 outlines implementation outcome-specific conceptual and definitional distinctions as well as proposed methods to measure these outcomes.

We will use Sekhon's 2017 Theoretical Framework for Acceptability (TFA)¹⁸ to assess the feasibility and acceptability of the intervention, informing interpretation of effectiveness overall (Aim 1), for sub-groups (Aim 2), and cost-effectiveness (Aim 3) by describing how acceptable the intervention is and how feasible the intervention is to deliver, from different stakeholder perspectives, and by describing the fidelity of the intervention.

Table 2. Aim 4 Qualitative and quantitative implementation science methods: conceptual and theoretical distinctions

Implementation outcome	Intervention stakeholder	Measures	Analysis

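### The Aim 2 clustering analysis uses the intervention arm alone, so it cannot separate men who do not benefit from men with a poor prognosis, and it can rank groups in the wrong order

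*Protocol*

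**What the plan says.** The Project Summary sets the objective: "identify populations of men who may not benefit from the intervention and require alternative support". Under Aim 2, Analyses, the quantitative paragraph opens with the primary analysis: "Among Aim 1 intervention group participants we will evaluate factors associated with declining the offer of a coach using logistic regression". It then turns to the analysis at issue: "Secondary within-group analyses of retention on ART using unsupervised machine-learning clustering methods will be conducted to determine the populations of men". The group it seeks is described as those "whose outcomes are least improved by engagement with a coach". Clusters are to be related to "the outcome of receiving the intervention but not being retained on ART, i.e. who does not respond well to the program".

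The Aim 2 section on expected outcomes gives the result prominence: "Crucially, we will identify populations of men who do not respond to the Coach Mpilo program", followed by "Findings will inform intervention scale-up and modifications to the program for maximum impact".

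A randomised 1:1 comparator exists. Under Randomization, the baseline survey precedes allocation, so both arms have it. Under Outcomes, retention is defined identically in both arms. The Aim 1 analyses are of overall effects, and no section plans an arm-by-subgroup or arm-by-cluster comparison.

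**The concern.** The stated target, men least improved by a coach, is a contrast: retention with a coach minus retention without one. The outcome analysed is an absolute one, and it cannot occur in a control man. The protocol joins the two and reads non-retention in the coached arm as non-response.

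A cluster's retention in the intervention arm is the sum of two unknowns, its retention under standard of care and the effect of the programme. Men with a poor outlook may show high non-retention while gaining a great deal. Men with a good outlook may show low non-retention while gaining nothing. At stake is the quantitative answer to who does not respond, which the protocol intends to use for scale-up and for changing the programme.

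**Working it through.** **Inputs.** From Aim 1, Sample size and power calculations: control retention of 50% (within an anticipated 40-60%), an effect of 10 percentage points, 80% power, 786 participants, recruitment target about 800. Allocation is 1:1 (Randomization).

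**Assumptions, not in the protocol.** Two-sided alpha of 0.05; two equal clusters, hence 200 men per cluster per arm; the cluster-specific rates below; 12-month retention as the outcome. The protocol's 40-60% is a range for overall control retention, not for subgroups.

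**The plan's own figure.** With variance 0.25 in both arms, n per arm = 2 × 0.25 × (1.960 + 0.842)² / 0.10² = 393 after rounding up, or 786 in total. This reproduces the stated size. The protocol gives no figure for the clustering analysis.

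**What the within-arm ranking measures.** For clusters A and B with control retention c and effect e:

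(c_B + e_B) − (c_A + e_A) = (c_B − c_A) + (e_B − e_A)

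Only the second bracket concerns benefit. The intervention arm supplies the sum.

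**Main illustration.** A goes from 40% to 55% (+15) and B from 60% to 65% (+5). The averages are (40 + 60)/2 = 50% and (55 + 65)/2 = 60%, as planned.

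- Within arm: non-retention is 45% in A and 35% in B. SE = √[(0.55 × 0.45 + 0.65 × 0.35)/200] = 0.0487. The chance that A ranks worse is Φ(0.10/0.0487) = 98%. A simulation of 200,000 trials gave 97.7%, with 0.5% ties.
- Between arms: the difference in effects is 10 points. SE = √[(0.2475 + 0.2275 + 0.24 + 0.24)/200] = 0.0691. The chance that A correctly shows the larger gain is Φ(0.10/0.0691) = 93% (92% by simulation).

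**Other cluster rates**, all averaging 50% and 60% (normal approximation):

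| A | B | Non-retained with coach, A / B | A ranked worse within arm | A shows larger gain between arms |
|---|---|---|---|---|
| 40→50 (+10) | 60→70 (+10) | 50% / 30% | almost 100% | 50% (no true difference) |
| 40→55 (+15) | 60→65 (+5) | 45% / 35% | 98% | 93% |
| 40→58 (+18) | 60→62 (+2) | 42% / 38% | 79% | 99% |
| 40→60 (+20) | 60→60 (0) | 40% / 40% | 50% | over 99% |
| 40→45 (+5) | 60→75 (+15) | 55% / 25% | almost 100% | 7% |
| 50→65 (+15) | 50→55 (+5) | 35% / 45% | 2% | 92% |

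In row 1 the benefit is identical, yet a within-arm test finds a difference with about 98.5% power. In row 4 a 20-point gain and no gain look the same. In rows 5 and 6 the within-arm ranking has the right direction.

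**Precision of the two-arm contrast.** In the main illustration the 95% interval for the interaction is 1.96 × 0.0691 = ±13.5 points, with about 30% power for 10 points. The detectable interaction at 80% power is about 2.80 × √(4 × 0.245/200) = 20 points. Reaching 80% power for 10 points needs about 4 × 0.955 × 2.80² / 0.10² ≈ 3,000 men. With four clusters of 100 + 100, each effect has SE √(0.25/100 + 0.24/100) = 7 points, and the difference between two of them about 7 × √2 = 10 points.

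**The case against.** Several points on the other side stand.

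- The analysis is labelled secondary. The primary Aim 2 analysis, on who declines a coach, is rightly confined to the intervention arm. Aim 2 also has participant and coach interviews. A reader might infer that Aim 2 as a whole cannot be answered; the documents do not support that. Only the quantitative part on non-response is affected.
- A reader might infer that the analysis measures prognosis alone, or must reverse the order. It measures prognosis plus effect, and rows 5 and 6 show the order can be right.
- A man not retained despite a coach may well need other support, whatever he gained from it. As a description of unmet need the analysis is sound. The fault lies in presenting it as who is least improved or does not benefit.
- A reader might infer that the population is restricted to men who took up a coach, a post-randomisation selection. Receipt stands in the outcome definition, not in a stated population restriction, so the text is ambiguous.
- A reader might link the clusters to the question of "whether the use of the intervention should be more narrowly targeted to specific population segments" and conclude that men would be excluded on this basis. That sentence belongs to the expected outcomes of Aim 3, and nothing says the Aim 2 clusters will decide it.

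One possible defence fails. The Aim 2 paragraph on participants refers to trial participants generally, which could include controls. But the analysis is called within-group, and its outcome is defined only for men given the intervention. Nor is this a detail left to an analysis plan: the protocol itself fixes the outcome and its interpretation.

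**Conclusion.** Wrong as written, and it should be corrected; it concerns a secondary analysis and leaves Aim 1 untouched. The within-arm analysis cannot separate poor prognosis from lack of benefit. Under the 40→55% and 60→65% illustration it puts the group with three times the gain last in about 98% of trials.

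The direction is right when the poorer-prognosis cluster also benefits less or when prognosis is equal. It would also be right if the poorer-prognosis cluster's extra gain exceeded the prognosis gap. With a 20-point gap, two equal clusters and an average effect of 10 points, that would require harm in the other cluster. Data from one arm cannot show which case holds.

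The size rests on the assumed cluster rates and on two equal clusters. The illustrations show what can happen, not how likely it is. That the quantity is not identified from one arm does not depend on them.

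**What to change.** 1. Form the clusters from baseline variables only, in both arms pooled and blind to outcome.
2. Within each cluster, estimate the difference in 12-month retention, intervention minus control, by assigned arm and with a confidence interval. Test the cluster-by-arm interaction. Label all of this exploratory.
3. Keep the within-arm analysis if wanted, but describe its result as men not retained despite the offer of a coach. Remove the wording that presents it as who is least improved, does not respond or does not benefit.

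The cost is a change of protocol and analysis-plan wording, since the control arm's baseline survey and retention data are already to be collected. The downside is precision: about 7 points of standard error per cluster of 100 + 100, and about 30% power for a 10-point interaction between two clusters of 200 per arm. The randomised contrast avoids mixing prognosis with effect, but it is noisy, so it should not drive targeting on its own. If the team does not want it, step 3 alone removes the wrong claim, and the objective in the Project Summary should then be narrowed to match.

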Inclusion criteria: Men living with HIV must meet the following criteria: (a) aged ≥ 18 years; (b) previously receiving HIV care at the study clinic; (c) missed their most recent ART clinic appointment by >28 days, (d) not planning to relocate to another region within the next 12 months; (e) able and willing to provide informed consent; (f) not currently taking ART. Importantly, agreement to be contacted by a coach (if selected) is not an eligibility criterion as our goal is to obtain generalizable evidence of the overall effectiveness of the Coach Mpilo program (uptake of communication with coaches will be explored in Aim 2).

Consenting process: Study staff will review the informed consent form with men who meet the inclusion criteria and answer any questions that men may have about study participation. The consent form (see Appendix A) includes a brief description of the Coach Mpilo intervention and the goals of the study. Staff will also obtain consent to review clinic records for participants. Those who provide informed consent and meet criteria for enrollment will proceed to randomization.

Data collection

Baseline survey: Study staff will administer a baseline questionnaire to obtain information on, among other things, participants' demographic characteristics, socio-economic status, health behaviour (HIV testing history, sexual behaviour, alcohol use), future outlook, internalized stigma and mental health. The baseline survey is found in Appendix B.

Follow-up survey: Study staff will contact participants at six months and administer an in-person

follow-up survey; many of the questions administered at baseline will be assessed again. The follow-up survey is found in Appendix C.

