Sample size and power calculations: We determined the target sample size based on statistical power to detect a clinically relevant effect of the intervention on the primary outcome of retention in care. We anticipate that Coach Mpilo will increase re-engagement and retention in HIV care (the primary outcome) by 10 percentage points. The Coach Mpilo pilot study found that 88% of men with coaches missed no clinic visits in their first seven months on ART, and 95% of men remained in care at seven months. This indicates 18-25% higher retention in care compared to several studies in South Africa that have found 30% drop out of care in the first six months of treatment.^{2,4,5} Given potential biases in the pilot data - there was no control group, data was self-report and not disaggregated by engagement in care at baseline - we hypothesize the intervention will increase retention in care by at least 10 percentage points. We performed power calculations under varying scenarios of the primary outcome in the control group. Based on existing data from clinics and prior research, we anticipate retention in care at 12 months to be 40-60%.^{12,13} With a sample size of 786 participants and 50% retention in care at 12 months, we will have 80% power to detect a difference of 10 percentage points between study groups. As a result, we will aim to recruit about 800 participants in the Aim 1 trial.

We also anticipate the intervention to: 1) improve mental health by reducing internalised stigma, increasing social support, and increasing hope; 2) reduce fears associated with living with HIV; 3) encourage HIV status disclosure.

Aim 2: Identify the populations of men who are *not* reached by and do not respond to Coach Mpilo

In the intervention group, we will measure intervention uptake and amount of engagement participants have with a coach. Primary quantitative analysis will assess the determinants of uptake within the intervention group to advance the limited evidence on sub-groups that are typically missed by peer-led interventions and therefore require different types of support. Qualitative interviews will also be conducted to better understand program uptake and engagement with a coach.

Participants: Aim 2 will be conducted with data collected from coaches and from Aim 1 trial participants.

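### The Aim 2 cluster analysis counts non-response as a joint event (took a coach and was not retained), so its ranking of clusters is confounded with uptake

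*Protocol*

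**What the plan says.** The analysis is in the Protocol, Aim 2, Analyses. The primary quantitative analysis comes first: "Among Aim 1 intervention group participants we will evaluate factors associated with declining the offer of a coach using logistic regression". The cluster analysis follows: "Secondary within-group analyses of retention on ART using unsupervised machine-learning clustering methods will be conducted". Its purpose is "to determine the populations of men whose outcomes are least improved by engagement with a coach". The composition of each cluster will be described, together with "the association between sub-group classification and the outcome of receiving the intervention but not being retained on ART". The protocol equates this event with non-response: "the outcome of receiving the intervention but not being retained on ART, i.e. who does not respond well to the program".

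Two other places show who is in the arm. The Aim 1 inclusion criteria say that "agreement to be contacted by a coach (if selected) is not an eligibility criterion". The opening of Aim 2 says "In the intervention group, we will measure intervention uptake and amount of engagement participants have with a coach", and that aim also plans about 15 interviews with men who decline a coach. Men without a coach are thus expected in the intervention arm by design.

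**The concern.** Receipt of the intervention sits inside the outcome and is not used to define the population. The last population named before the cluster analysis is the whole intervention arm, and no narrower one is given. On that literal reading, the men who do not have the event are a mixture: men with a coach who were retained, men without a coach who were retained, and men without a coach who dropped out. The third group counts on the favourable side although those men were neither reached nor retained.

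The protocol wants this analysis to show who does not respond well. It intends Aim 2 to inform scale-up and changes to the program, and under Aim 3 it raises the possibility of targeting narrower population segments. If the score falls when uptake falls, a cluster of men who rarely take a coach can look like a group that responds well. A cluster that takes coaches readily can look like a failure.

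**Working it through.** The protocol states no figure for this analysis, so there is nothing to reproduce. The check is algebra, followed by assumed values.

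**Inputs**
- Outcome: took the intervention and was not retained (Aim 2, Analyses).
- Uptake by cluster, *u*: not given anywhere. Assumed between 0% and 90%.
- Retention among takers by cluster, *r*: not given. The sample size section says "we anticipate retention in care at 12 months to be 40-60" per cent. Used as a rough guide, this suggests non-retention of 40% to 60%.
- Retention among men without a coach: not given. Assumed 50% where needed.

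**Formulas**
- Joint event rate in a cluster = *u* × (1 − *r*).
- Non-retention among takers = 1 − *r*.
- Let cluster A be worse than cluster B among takers, so that *r*A < *r*B. A looks better on the joint event when *u*A(1 − *r*A) < *u*B(1 − *r*B), that is, when *u*A/*u*B < (1 − *r*B)/(1 − *r*A).

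**Thresholds for reversal**
- Non-retention among takers 60% v 40%: 0.40/0.60 = 0.67.
- Non-retention among takers 50% v 40%: 0.40/0.50 = 0.80.

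**Assumed cases**

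| Uptake A v B | Non-retention among takers A v B | Joint event A v B | Uptake ratio | Order |
|---|---|---|---|---|
| 40% v 90% | 60% v 40% | 0.40 × 0.60 = 24% v 0.90 × 0.40 = 36% | 0.44 | reversed |
| 60% v 90% | 50% v 40% | 0.60 × 0.50 = 30% v 0.90 × 0.40 = 36% | 0.67 | reversed |
| 80% v 90% | 50% v 40% | 0.80 × 0.50 = 40% v 0.90 × 0.40 = 36% | 0.89 | kept |
| 30% v 90% | 40% v 40% | 0.30 × 0.40 = 12% v 0.90 × 0.40 = 36% | 0.33 | no true difference, 24 points from uptake alone |
| 0% in A | any | 0% in A | 0 | A always scores best |

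In the first case, A has 20 points more non-retention among takers but ranks 12 points better.

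**How the reading changes the answer.** Take uptake of 30% v 90% and non-retention among takers of 60% v 40%.
- Joint event over the whole arm: 0.30 × 0.60 = 18% v 0.90 × 0.40 = 36%.
- Takers only: 60% v 40%.
- All intervention men, with 50% non-retention among men without a coach: 0.18 + 0.70 × 0.50 = 53% v 0.36 + 0.10 × 0.50 = 41%.

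The last two measures both put A as worse. Only the joint event puts B as worse.

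**The case against.** The strongest reply is that the protocol gives no denominator here, and that two other readings remove the problem.

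- *Takers only.* The stated purpose concerns men improved by engaging with a coach, and men who never engaged cannot be improved by it. On this reading the outcome is simply non-retention among takers.
- *Receipt means assignment.* The Randomization paragraph describes the whole intervention group as receiving the program. On this reading the outcome is non-retention in the arm, and uptake does not enter the rate as a multiplier.

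Both are possible, but neither is stated. Each also makes the receipt clause redundant, because everyone analysed would satisfy it. The assignment reading sits badly with a purpose framed as engagement with a coach.

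It can also be said that analysis sets for a secondary analysis belong in a SAP, which is not at hand. That would answer a complaint about a missing detail. Here the protocol states the outcome and its interpretation, and the stated outcome is the difficulty.

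Some of the reply does stand, and it rules out three stronger conclusions that a reader might draw.

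- *That the ranking will reverse.* The documents give no uptake rates, and the 80% v 90% case above keeps the order.
- *That Aim 2 merges unreached men with non-responders and becomes uninterpretable.* Declining a coach is the primary quantitative analysis and has its own logistic model. Uptake and engagement are measured, cluster composition is described, and decliners, early stoppers and supported men are interviewed separately. Hard-to-engage men would still be identified.
- *That analysing takers only would show who benefits least.* It would not. Taking a coach happens after randomisation, and a comparison within one arm has no control group.

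**Conclusion.** The point holds in a limited form. As worded, and applied to the whole intervention arm, the outcome measures uptake multiplied by non-retention among takers, so the ranking of non-responding clusters is confounded with uptake. It can reverse when uptake differs enough: below a ratio of 0.67 for assumed non-retention of 60% v 40% among takers, and below 0.80 for 50% v 40%. Even with equal non-retention of 40% among takers, uptake of 30% v 90% produces a spurious gap of 24 points.

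This rests on the literal reading of the denominator and on assumed cluster rates. The algebra does not depend on those rates, but whether a reversal occurs in this trial does. The point does not touch the primary outcome, the sample size or the uptake model. It deserves correction because the protocol intends Aim 2's account of non-responders to inform scale-up.

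**What to change.** Drop the joint event as the outcome of the association analysis. For each cluster, report:

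1. uptake among all intervention men, taken from the coach log book under a definition of uptake fixed in advance;
2. non-retention among men who took a coach, with the denominator stated;
3. non-retention among all intervention men, at the same time point.

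Label the second figure as descriptive. It conditions on a post-randomisation variable and does not by itself show who is least improved by a coach. That question needs clusters built from baseline variables and compared between the randomised arms.

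The cost is a change of wording in the protocol or SAP. The log book, the clinic records and the baseline survey already supply the data. The downside is that the second figure rests on fewer men and will be less precise, most of all in clusters with low uptake.
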